11.4 CASE REPORT FORMS

All patient data relating to the treatment protocol will be recorded on eCRFs to be provided by the sponsor through the EDC system. The investigator is responsible for verifying that all data entries in the eCRFs are accurate and correct by electronically signing the completed eCRF casebook submitted to the sponsor. The investigator must maintain and retain accurate documentation that supports the information entered into the EDC system for source document verification and possible regulatory inspection.

11.5 RETENTION AND REVIEW OF RECORDS

Records and documents pertaining to the conduct of this treatment protocol, including eCRFs, source documents, consent forms, regulatory documents, clinical laboratory results, calibration logs, or reports (including, but not limited to, all laboratory results and ECG reports), and medication inventory records in all formats (including, but not limited to, written, electronic, magnetic, and optical records, and scans, x-rays, and ECGs) must be retained by the investigator for a period of at least 15 years after treatment protocol completion unless local regulations or institutional policies require a longer retention period or otherwise notified in writing by the sponsor.

No treatment protocol records shall be destroyed without notifying the sponsor and providing the sponsor the opportunity to arrange long-term storage for such treatment protocol records or authorizing in writing the destruction of records after the required retention period.

The investigator must permit access to any documentation relating to the treatment protocol upon request of the sponsor or applicable regulatory authorities. If the investigator for the treatment protocol retires, relocates, or for other reasons withdraws from the responsibility of keeping the treatment protocol records, custody must be transferred to a suitable alternate custodian employee of the institution or to a suitably qualified and responsible third party. The sponsor must be notified in writing of the name and address of the new custodian in advance of the transfer.

- A statement describing the extent, if any, to which confidentiality of records identifying the patient will be maintained and noting the possibility that the FDA, the sponsor, the IRB/EC, or an authorized contract research organization may inspect the records
- For research involving more than minimal risk, an explanation of whether any medical treatment is available if injury occurs and, if so, what it consists of or where further information may be obtained
- An explanation of whom to contact, including the relevant telephone number, for answers to pertinent questions about the research and the research patient's rights and whom to contact in the event of a research-related injury to the patient. (Note: In some cases, it may be necessary to identify a person other than the investigator as the contact. The guidance of the IRB/EC may be required)
- A statement that participation is voluntary, that refusal to participate will involve no penalty or loss of benefits to which the patient is otherwise entitled, and that the patient may discontinue participation at any time without penalty or loss of benefits to which the patient is otherwise entitled

- A statement that the particular treatment or procedures may involve risks to the patient (or to the embryo or fetus if the patient is, or may become, pregnant) that are at present unforeseeable
- The expected circumstances for which the patient's participation may be terminated by the investigator without regard to the patient's consent
- Any additional costs to the patient that may result from participation in the research
- The consequences of a patient's decision to withdraw from the research and procedures for an orderly termination of the patient's participation
- A statement that significant new findings developed during the course of the research that may relate to the patient's willingness to continue participation will be provided to the patient
- The approximate number of patients involved in the treatment protocol
- A statement of permission, providing consent for the patient to participate (eg, "I agree to participate . . .")
- A place for the patient's signature and date of signing the ICF
- A statement indicating that information about this treatment protocol has been, or will be, entered into a databank that is publicly accessible at www.ClinicalTrials.gov.

A copy of the signed consent form must be given to the patient.

17.0 CHANGES TO ANALYSES SPECIFIED IN PROTOCOL22

3.0 **LIST OF ABBREVIATIONS**

ADT	antidepressant therapy
AE	adverse event
eCRF	electronic case report form
ET	early termination
ICF	informed consent form
IP	investigational product
IV	intravenous(ly)
MDD	major depressive disorder
OLTP	open-label treatment period
SAE	serious adverse event
SAP	statistical analysis plan
SD	standard deviation
SOC	system organ class
TEAE	treatment-emergent adverse event
TESAE	treatment-emergent serious adverse event

4.0 **INTRODUCTION**

This statistical analysis plan (SAP) provides a more technical and detailed elaboration of the statistical analyses of efficacy and safety data as outlined and/or specified in the final study protocol, dated 03 Jul 2018. Specifications of tables, figures, and data listings are contained in a separate document.

RAP-MD-99 is a multicenter, open-label extended access treatment protocol in adult participants with MDD who completed lead-in studies RAP-MD-04, RAP-MD-05, or RAP-MD-33 study within approximately 1 month of Visit 1, or RAP-MD-06 at any time prior to Visit 1. The final visit from the lead-in study may serve as the first visit of protocol RAP-MD-99 where practical to maintain continuity of treatment. In other cases, the first visit of RAP-MD-99 may be conducted independent of the final visit of the lead-in study.

Following consent at the initial visit, participants will be screened and those who meet entry criteria may enter the OLTP and receive the first dose of open-label treatment (rapastinel). Consent, screening and dosing may all be conducted in a single visit at the discretion of the investigator to facilitate continuity of treatment. Participants may also enter RAP-MD-99 at a visit independent of the lead-in study occurring no more than 21 days after completion of the lead-in study.

During the OLTP participants will return to the study center for visits at which administration of rapastinel and wellness check are conducted. Visits should typically be spaced weekly or biweekly but may be up to 4 weeks apart (based on investigator discretion).

Each participant will be treated until the investigator discontinues them at their discretion, the participant discontinues for other reasons, or until the treatment protocol or study center is terminated by the Sponsor.

Appropriate safety follow-up upon discontinuation of participants from treatment will be at the discretion of the investigator.

This treatment protocol will be conducted as an Open-label Treatment Period (OLTP) of indeterminate duration.

There is no predetermined limit specified for the number of participants that may be enrolled in the OLTP.

The treatment protocol will be ended upon drug availability following marketing approval, termination of rapastinel development, or if sponsor determines that treatment protocol termination is appropriate for other reasons.

5.0 **OBJECTIVES**

The objective of this treatment protocol is to provide continued access to rapastinel for participants with MDD who have completed specified prior rapastinel studies.

6.0 PARTICIPANT POPULATIONS

Two analysis populations are defined for this study, as specified in the following subsections. All participants will be combined into one treatment group: Rapastinel 450 mg, for statistical analyses purposes.

6.1 ENROLLED PARTICIPANTS POPULATION

The Enrolled Participants Population will consist of all participants who signed the RAP-MD-99 informed consent form (ICF).

6.2 OPEN-LABEL SAFETY POPULATION

The Open-label Safety Population will consist of all participants who signed the RAP-MD-99 ICF and who received at least 1 dose of open-label rapastinel during the OLTP of the protocol.

7.0 STUDY PARTICIPANTS

7.1 PARTICIPANT DISPOSITION

The number and percentage of participants in each enrollment category (RAP-MD-04 Completer, RAP-MD-05 Completer, RAP-MD-06 Completer, RAP-MD-33 Completer), participants who completed the RAP-MD-99 study, and who prematurely discontinued from the OLTP will be summarized overall and by reasons for premature discontinuation for the Enrolled Participants Population.

8.0 **DEMOGRAPHICS AND OTHER BASELINE CHARACTERISTICS**

Demographic parameters (eg, age, race, ethnicity, sex) and baseline characteristics (eg, weight, height, body mass index) will be summarized for the Open-label Safety Population.

Prior medication is defined as any medication taken within 12 months prior to the date of the first dose of open-label rapastinel in RAP-MD-99. *Concomitant medication* during the OLTP is defined as any medication taken on or after the date of the first dose of open-label rapastinel during the OLTP through the early termination or a follow-up visit that occurs up to 30 days after the last known dose of open-label rapastinel. The *WHO Drug Dictionary Enhanced*, will be used to classify prior and concomitant medications by therapeutic class and drug name. A data listing for the prior and concomitant medications will be provided.

9.0 **EXTENT OF EXPOSURE AND TREATMENT COMPLIANCE**

9.1 **EXTENT OF EXPOSURE**

Exposure to open-label rapastinel for the Open-label Safety Population during the OLTP will be summarized for treatment duration by weekly intervals, calculated from the number of days from the date of the first dose of open-label rapastinel taken to the date of the last dose taken during the OLTP, inclusive. Summary statistics will also be presented.

Participant-years, defined as the sum of the treatment duration of all participants divided by 365.25, will also be summarized.

9.2 **MEASUREMENT OF TREATMENT COMPLIANCE**

Not applicable.

10.0 **EFFICACY ANALYSES**

Not applicable.

11.0 SAFETY ANALYSES

The safety analyses for the OLTP will be performed using the Open-label Safety Population. The summarization will be overall for the OLTP without consideration for dosing frequency.

Safety parameters will be limited to AEs.

11.1 ADVERSE EVENTS

AEs will be coded using the *Medical Dictionary for Regulatory Activities (MedDRA)*.

An AE (classified by preferred term) that occurs during the OLTP will be considered a treatment-emergent adverse event (TEAE) if it was not present before the date of the first dose of IP in the OLTP or was present before the first dose of IP of the first lead-in study and increased in severity during the OLTP. If more than 1 AE is reported before the date of the first dose of IP in the OLTP and coded to the same preferred term, the AE with the greatest severity will be used as the benchmark for comparison with the AEs occurring during the OLTP that were also coded to that preferred term. An AE that occurred more than 30 days after the date of the last dose of open-label IP will not be counted as a TEAE. An AE that becomes serious during the OLTP will also be considered as TEAE.

The incidence of common (in $\geq 2\%$ of participants) TEAEs during the OLTP will be summarized by preferred term and will be sorted by decreasing frequency.

An SAE that occurred between the date of the first dose of the open-label IP and 30 days after the date of the last dose of IP, inclusive, will be considered a treatment-emergent SAE (TESAE).

The incidence of death, TEAE, treatment-related TEAE, TESAE, TEAEs leading to premature discontinuation of IP during the OLTP will be summarized.

Listings will be presented for all participants with SAEs, participants with AEs leading to discontinuation, and participants who died (if any).

12.0 **HEALTH ECONOMICS AND OUTCOMES ANALYSES**

Not applicable.

13.0 **INTERIM ANALYSIS**

No interim analysis is planned for this treatment protocol.

14.0 **DETERMINATION OF SAMPLE SIZE**

Not applicable.

15.0 **COMPUTER METHODS**

Statistical analyses will be performed using [REDACTED]

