9.5.2.1 Adverse Events

An AE is any untoward medical occurrence in a patient or clinical investigation patient administered a pharmaceutical product and which does not necessarily have to have a causal relationship with this treatment. An AE can therefore be any unfavorable and unintended sign (including an abnormal laboratory finding, for example), symptom, or disease temporally associated with the use of a medicinal product, whether or not considered related to the medicinal product (ICH-E2A).

For the purpose of the study center's data collection responsibilities, any untoward event that was reported from the time the patient signed the ICF until 30 days after the last known dose of IP (if the final visit does not occur) is to be considered an AE.

Examples of AEs are as follows:

- Changes in the general condition of the patient
- Subjective symptoms offered by or elicited from the patient
- Objective signs observed by the investigator or other study center personnel
- All diseases that occur after signing informed consent, including any change in severity or frequency of pre-existing disease
- All clinically relevant abnormalities in laboratory values or clinically relevant physical findings that occur during the treatment protocol

Please note that medical procedures scheduled prior to consenting, but occurring during the treatment protocol should not be captured as AEs, but should be listed in the medical history if related to a pre-existing condition.

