9.7.6 Safety Analyses

The safety analyses for the OLTP will be performed using the Open-label Safety Population. The summarization will be overall for the OLTP without consideration for dosing frequency.

Safety parameters will be limited to AEs.

For each safety parameter, the baseline of the lead-in study will be used as the baseline for all analyses of that safety parameter, unless stated otherwise.

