9.7.6.1 Adverse Events

AEs will be coded by system organ class (SOC) and preferred term using the *Medical Dictionary for Regulatory Activities*.

An AE (classified by preferred term) that occurs during the OLTP or thereafter will be considered a treatment-emergent adverse event (TEAE) if it was not present before the date of the first dose of IP in the OLTP or was present before the first dose of IP of the first lead-in study and increased in severity during the OLTP or thereafter. If more than 1 AE is reported before the date of the first dose of IP in the OLTP and coded to the same preferred term, the AE with the greatest severity will be used as the benchmark for comparison with the AEs occurring during the OLTP that were also coded to that preferred term.

The number and percentage of patients reporting TEAEs during the OLTP will be tabulated by SOC, preferred term, and further categorized by severity and causal relationship to the IP. If more than 1 AE is coded to the same preferred term for the same patient during the OLTP, the patient will be counted only once for that preferred term using the most severe and most related occurrence for the summarization by severity and by causal relationship to the IP.

The incidence of common ($\geq 2\%$ of patients) TEAEs during the OLTP will be summarized by preferred term and will be sorted by decreasing frequency.

An SAE that occurred between the date of the first dose of the IP and 30 days after the date of the last dose of IP, inclusive, will be considered an on-therapy SAE. The number and percentage of patients who had on-therapy SAEs during the OLTP will be summarized by preferred term and sorted by decreasing frequency.

The number and percentage of patients who had fatal on-therapy SAEs during the OLTP will be summarized by preferred term and sorted by decreasing frequency.

The incidence of TEAEs leading to premature discontinuation of IP during the OLTP will be summarized by preferred term and will be sorted by decreasing frequency.

Listings will be presented for all patients with SAEs, patients with AEs leading to discontinuation, and patients who died (if any).

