16.7 MISSING DATE INFORMATION FOR ADVERSE EVENTS

The following imputation rules only apply to cases in which the start date for an AE is incomplete (ie, partly missing).

Missing month and day

- If the year of the incomplete start date is the same as the year of the first dose of open-label IP, the month and day of the first dose of open-label IP will be assigned to the missing fields.
- If the year of the incomplete start date is before the year of the first dose of open-label IP, *31 Dec* will be assigned to the missing fields.
- If the year of the incomplete start date is after the year of the first dose of open-label IP, *01 Jan* will be assigned to the missing fields.

Missing month only

- If only the month is missing, the day will be treated as missing and both the month and the day will be replaced according to the above procedure.

Missing day only

- If the month and year of the incomplete start date are the same as the month and year of the first dose of open-label IP, the day of the first dose of open-label IP will be assigned to the missing day.
- If either the year of the incomplete start date is before the year of the date of the first dose of open-label IP or if both years are the same but the month of the incomplete start date is before the month of the date of the first dose of open-label IP, the last day of the month will be assigned to the missing day.
- If either the year of the incomplete start date is after the year of the date of the first dose of open-label IP or if both years are the same but the month of the incomplete start date is after the month of the date of the first dose of open-label IP, the first day of the month will be assigned to the missing day.

If the stop date is complete and the imputed start date as above is after the stop date, the start date will be imputed by the stop date.

If the start date is completely missing and the stop date is complete, the following algorithm will be used to impute the start date:

- If the stop date is after the date of the first dose of open-label IP, the date of the first dose of open-label IP will be assigned to the missing start date.
- If the stop date is before the date of the first dose of open-label IP, the stop date will be assigned to the missing start date.

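### The two limbs of the TEAE definition use different reference dates, so a nonserious AE that first appears between the first lead-in dose and the first OLTP dose and then worsens is not counted

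*SAP*

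**What the plan says.** SAP 11.1 classifies adverse events by preferred term and gives two ways for an OLTP event to be a TEAE. The first is that it was not present before the first IP dose in the OLTP. The second is that it "or was present before the first dose of IP of the first lead-in study and increased in severity during the OLTP". Protocol 9.7.6.1 has the same pair of dates, with a longer window: "or was present before the first dose of IP of the first lead-in study and increased in severity during the OLTP or thereafter".

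Four other provisions bear on the reading:

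- **Severity benchmark.** The next sentence in both documents begins "If more than 1 AE is reported before the date of the first dose of IP in the OLTP". It takes the most severe of those earlier events with the same term as the comparator.
- **Seriousness.** The SAP adds a route that the protocol's definition lacks: "An AE that becomes serious during the OLTP will also be considered as TEAE".
- **Default baseline.** Protocol 9.7.6 says that "the baseline of the lead-in study will be used as the baseline for all analyses of that safety parameter, unless stated otherwise".
- **Partial start dates.** SAP 16.7 imputes by reference to the first open-label dose, for example "If the year of the incomplete start date is before the year of the first dose of open-label IP".

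The flag feeds the main outputs of SAP 11.1: "The incidence of death, TEAE, treatment-related TEAE, TESAE, TEAEs leading to premature discontinuation of IP during the OLTP will be summarized". It also feeds the table of preferred terms reported by at least 2% of participants. SAP 17.0 does not mention the definition.

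**The concern.** The two limbs should cover new events and worsened events without leaving a space between them. Here the first looks back from the first open-label dose and the second from the first dose of the first lead-in study. Every participant comes from a lead-in study, so everyone has an interval between those dates. For RAP-MD-06 completers that interval has no upper limit.

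Worsening on open-label drug therefore counts if the condition predates the lead-in study, but not if it began during or after that study. Neither document gives a reason.

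The safety analysis is limited to adverse events, and SAP 17.0 has already cut the TEAE summaries back to the 2% table. The listings named in SAP 11.1 cover serious events, discontinuations and deaths. A nonserious event in the gap that does not lead to discontinuation therefore appears in no output named there. The separate specification of tables and listings mentioned in SAP 4.0 was not available and may show it.

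**Working it through.** The plan states no figure to reproduce: sample size is not applicable and the analysis is descriptive. The check is of the rule's logic, followed by illustrations on assumed rates.

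**1. The rule case by case.** Let A be a term present before the first lead-in dose, B a term first present between that dose and the first OLTP dose, and C a term first present on or after the first OLTP dose. The table gives TEAE status for events that stay nonserious.

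| Case | As written | OLTP date in both limbs | Lead-in date in both limbs |
|---|---|---|---|
| A, unchanged | no | no | no |
| A, worsened | yes | yes | yes |
| B, unchanged | no | no | yes |
| **B, worsened** | **no** | **yes** | **yes** |
| C | yes | yes | yes |

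Under the SAP, all five cases count if the event becomes serious. Over the 10 cells (5 cases, serious or not) the totals are 2 + 5 = 7, 3 + 5 = 8 and 4 + 5 = 9. Under the protocol, which has no seriousness sentence, they are 4, 6 and 8. These counts test logic and are not frequencies. The single SAP cell changed by using the OLTP date throughout is B, worsened, nonserious.

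**2. The benchmark sentence.** It applies only when more than one earlier event shares the term, and it selects a comparator. It adds no route to TEAE status, so it does not close the gap. Its comparators do come from everything before the first OLTP dose, which does not fit a lead-in date in the worsening limb.

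**3. The imputation rules.** All 8 bulleted rules in SAP 16.7 that name a reference date use the first open-label dose; none uses the lead-in dose. Assume a first lead-in dose on 15 Mar 2017 and a first OLTP dose on 10 Sep 2018. A start date known only as 2017 becomes 31 Dec 2017. Any true onset from 1 Jan to 14 Mar 2017 (31 + 28 + 14 = 73 days) then moves from A to B. A start date known only as Mar 2017 becomes 31 Mar 2017, which moves 14 possible days. With no earlier stop date, such an event fails the worsening limb even if it worsens.

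**4. Effect on one preferred term.** N = 1800 is the planned approximate maximum in the Protocol synopsis, so the 2% cut is 0.02 × 1800 = 36 participants. Let p be the assumed share with a nonserious case-B event of that term that worsens.

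- p = 0.1%: 0.001 × 1800 = 1.8, about 2 missing
- p = 0.5%: 0.005 × 1800 = 9 missing
- p = 1%: 0.01 × 1800 = 18 missing

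At p = 0.5%, 36 to 44 true cases (2.0% to 2.4%) become 27 to 35, all below 36.

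**5. Effect on overall TEAE incidence.** The shortfall is q(1 − r), where q is the share of participants with at least one such event and r the share of those with another qualifying TEAE.

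- q = 0.5%, r = 90%: 0.005 × 0.1 = 0.05 percentage points, about 1 of 1800
- q = 5%, r = 50%: 0.05 × 0.5 = 2.5 percentage points, 45 of 1800

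**The case against.** The strongest objection is that the gap may not reach the outputs. Protocol 9.5.2.1 treats a change in severity of pre-existing disease as an adverse event. If sites record each worsening as a new event with OLTP onset, and presence is judged event by event, the first limb counts it. The definition, however, says events are classified by preferred term, and on that reading an earlier occurrence defeats the first limb whatever the new record's onset date.

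It is also fair that the documents do not show how lead-in records enter the flag. Collection in this protocol covers "any untoward event that was reported from the time the patient signed the ICF until 30 days after the last known dose of IP", and consent and first dose may fall on one visit. Naming the lead-in dose in the definition implies that the records are linked, but the derivation is not given. Nor do the documents say whether events between lead-in completion and consent are recorded.

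Three further points stand as qualifications:

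- **Imputation works both ways.** A partial date in the same year, or the same month and year, as the first OLTP dose is set to that dose. A case-B event with no earlier stop date is then counted as new. This acts through the first limb and leaves the defect in the second.
- **The illustrations are assumption-driven.** The loss of 9 cases in step 4 is 20% to 25% of the term's true cases (9/44 to 9/36). At 0.1%, only terms with 36 or 37 cases fall off the table. The 73 days assume that lead-in records reach back that far. Protocol 9.1 sets no enrolment limit, so 1800 is a planning figure.
- **The stakes are bounded.** This is a single-arm access protocol with descriptive analyses.

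The benchmark sentence suggests a drafting slip rather than a deliberate exclusion. That is a reason to correct the sentence, because a TEAE flag should not depend on a programmer's guess at the intent.

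**Conclusion.** The concern holds. As written, a nonserious event whose preferred term is first present between the first lead-in dose and the first OLTP dose, and which worsens in the OLTP, is not a TEAE. Under the protocol's wording, one that becomes serious is not a TEAE either.

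Relative to a consistent date in both limbs, the error runs in one direction. It understates TEAEs, treatment-related TEAEs, TEAEs leading to discontinuation and the 2% table. The overall rows change only for participants with no other qualifying TEAE. Within a single term there is less offset, because on the preferred-term reading a case-B term can count only by becoming serious.

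The size cannot be estimated from the documents, and the figures above are illustrations only. The conclusion itself rests on the wording and on applying presence by preferred term, not on those rates. It should be fixed, but it does not hide serious events, deaths or listed discontinuations.

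**What to change.** In SAP 11.1, change the date in the worsening limb so that it reads: *or was present before the date of the first open-label dose and increased in severity during the OLTP*. Keep the existing 30-day cut-off. List this in SAP 17.0 as a change from Protocol 9.7.6.1 and from the default baseline of Protocol 9.7.6, and align the protocol wording at its next amendment.

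This date agrees with the first limb, the benchmark comparators and the SAP 16.7 imputation rules. Using the lead-in date in both limbs would also close the gap. It would, however, need new imputation rules and would count events that began in the lead-in study and continued unchanged.

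The cost is one SAP sentence, one SAP 17.0 entry and an update to the TEAE flag, with no stand-alone protocol amendment and no new data collection. Reported TEAE incidence may rise.

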9.2 DISCUSSION OF TREATMENT PROTOCOL DESIGN

This multicenter, open-label, treatment protocol was designed taking into account prior studies that established rapastinel efficacy and safety in adult patients with MDD.

Study centers will have experience with the patient population and will be encouraged to apply available guidelines to minimize patient risk or distress. All study centers will have experience with rapastinel in the lead-in studies and all patients will have participated in the lead-in studies.

Dose selection information is presented in Section 9.4.5. The planned dosing regimen is based on experience from previous rapastinel studies.

In the event of insufficient therapeutic response or worsening of the patient's initial condition, the IP may be discontinued at the investigator's discretion and an alternative treatment begun.

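### A non-serious lead-in adverse event that resolved and recurs in the OLTP at the same or lower severity is, on the natural reading, not counted as a TEAE

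*SAP*

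**What the plan says.** SAP 11.1 builds the definition as follows.

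- Unit of classification: "An AE (classified by preferred term) that occurs during the OLTP will be considered a treatment-emergent adverse event (TEAE" (the quote stops at the abbreviation). The preferred term is classified, not the episode.
- First limb, new events: "if it was not present before the date of the first dose of IP in the OLTP".
- Second limb, worsening: "was present before the first dose of IP of the first lead-in study and increased in severity during the OLTP".
- Benchmark: "If more than 1 AE is reported before the date of the first dose of IP in the OLTP" under the same preferred term, then "the AE with the greatest severity will be used as the benchmark for comparison with the AEs occurring during the OLTP".
- Exceptions and limits: an event that becomes serious in the OLTP counts in any case, and events starting more than 30 days after the last dose do not count. A treatment-emergent SAE is defined by its date alone, with no comparison to earlier events.

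Protocol 9.7.6.1 has the same first limb ("was not present before the date of the first dose of IP in the OLTP"), the same worsening limb and the same benchmark. Protocol 9.2 states that "all patients will have participated in the lead-in studies". Protocol 9.3.1 lets RAP-MD-06 completers enter whatever their completion date. SAP 11.0 limits safety parameters to adverse events, and SAP 17.0 leaves the table of TEAEs in at least 2% of participants as the only TEAE summary by preferred term.

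**The concern.** Neither document says how far back an earlier event may lie, or that it must still be ongoing at the first open-label dose. Suppose a participant had one moderate headache during a lead-in study, which resolved. Mild or moderate headaches then begin after open-label injections. On the natural reading the term was already present, the severity has not risen, and none of the new headaches is a TEAE.

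Every participant comes from a lead-in study, so the rule can touch anyone with an adverse-event history. For RAP-MD-06 completers the look-back may be long. Adverse events are the only outcome analysed, so the definition of a TEAE decides most of what the report will show. The rule also sits awkwardly with the plan's own approach elsewhere. Protocol 9.5.2.1.1 treats a positive rechallenge as evidence of causality, whereas this rule can remove a recurrence on re-dosing from the treatment-related count. SAP 16.5 and 16.6 resolve missing severity and causality towards over-reporting, whereas this rule works towards under-reporting.

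**Working it through.** **Step 1: apply the rule.** The plan states no figure that depends on this point, so there is none to reproduce. Take an event that first arose during the lead-in study, resolved, and recurs in the OLTP without becoming serious. Three earlier severities and three recurrence severities give 9 combinations. The worsening limb can be read in two ways: literally (it covers only events present before the first lead-in dose), or as the benchmark sentence implies (any event before the OLTP is compared on severity).

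| Recurrence compared with earlier event | Combinations | TEAE, literal | TEAE, benchmark reading | TEAE if judged by onset |
|---|---|---|---|---|
| Same or lower severity | 6 | 0 | 0 | 6 |
| Higher severity | 3 | 0 | 3 | 3 |

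The first row is the point made here. It is 0 of 6 on both readings, so putting both limbs on one reference date does not cure it. The second row is the separate reference-date problem in the same sentence.

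**Step 2: which words exclude the recurrence.** The benchmark sentence applies only when more than one earlier event shares the term. With a single earlier event, the first limb does the excluding. With several, the first limb and the benchmark both do.

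**Step 3: size for one preferred term.** All rates below are assumptions. Let q be the share of dosed patients who had the term before the OLTP, r the share of them in whom it recurs, f the share of the others in whom it first occurs, and w the share of recurrences worse than before.

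- True incidence = q·r + (1 − q)·f
- Counted incidence = (1 − q)·f + q·r·w
- Loss = q·r·(1 − w) / true incidence

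With r = 0.30, f = 0.08, w = 0.20:

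| q | True | Counted | Loss |
|---|---|---|---|
| 0.10 | 0.030 + 0.072 = 0.102 | 0.072 + 0.006 = 0.078 | 0.024/0.102 = 24% |
| 0.20 | 0.060 + 0.064 = 0.124 | 0.064 + 0.012 = 0.076 | 0.048/0.124 = 39% |
| 0.30 | 0.090 + 0.056 = 0.146 | 0.056 + 0.018 = 0.074 | 0.072/0.146 = 49% |

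With r = f = 0.08 the true incidence is 0.08 and the loss reduces to q·(1 − w): 0.10 × 0.80 = 8% and 0.20 × 0.80 = 16%. The assumed excess of recurrence over first occurrence therefore drives much of the result.

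These figures let worsened recurrences count, so they assume the reference dates have been aligned. On the literal text w = 0, and the middle row of the table becomes 0.060/0.124 = 48%.

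**Step 4: the 2% table.** Take 1,800 as an illustration; the Protocol synopsis gives it as approximate maximum enrolment, not as the number dosed. The cut-off is 0.02 × 1,800 = 36 participants. A term with true incidence p leaves the table once the uncounted share exceeds 1 − 0.02/p: 20% at p = 2.5%, 33% at 3%, 50% at 4%, 60% at 5%, 80% at 10%. For example, p = 2.5% is 45 participants; with 25% uncounted, about 34 remain (1.9%) and the term drops out. Only terms fairly near the threshold are at risk of disappearing; commoner terms stay but are understated.

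**The case against.** The strongest reply is that *present* is undefined, and a resolved event could be said to be no longer present at the first open-label dose. On that reading recurrences would count. The text leans the other way, because classification is by preferred term and the benchmark draws on events reported at any time before that dose. The ambiguity stands, though, and is itself a reason to define the word before programming.

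Second, the rule is prespecified in both documents, and counting only what is new or worse than a patient's history is a coherent choice. That is fair. But the SAP already counts SAEs by date alone, and a recurrence that starts after an open-label dose is what a reader of a TEAE table expects to find there.

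Third, the data are not lost. SAEs are counted by date, deaths are summarised, and the listing of events leading to discontinuation covers all AEs, not only TEAEs. Protocol 9.5.2.1.4 has events recorded in the eCRF whatever their causality, and Protocol 9.8 provides a DSMB. This stands. The gap lies in the tabulation of non-serious recurrences. The listings named in SAP 11.1 would not show those that do not lead to discontinuation, although listing specifications are held in a separate document.

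Two stronger inferences are tempting and are not supported. One is that the suppressed events are rapastinel's own reactions. Protocol 9.2 says patients took part in lead-in studies; the documents do not describe the arms or show that each earlier event occurred on rapastinel. The other is that overall TEAE incidence falls by 24-49%. Those figures are for one term, and a participant with any other qualifying event still counts in the any-TEAE row.

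**Conclusion.** The concern holds. On the natural reading of SAP 11.1 and Protocol 9.7.6.1, a resolved event that recurs non-seriously at the same or lower severity is not a TEAE, and aligning the reference dates does not change that. Compared with counting by onset, preferred-term TEAE counts, the 2% table and treatment-related TEAEs can only be lowered. The summarised incidence of TEAEs leading to discontinuation is subject to the same rule.

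The direction is clear, but the size cannot be derived from the documents. Losses of 24-49% or 8-16% for a single term are illustrations that depend on the assumed prevalence, recurrence and worsening rates. The study is descriptive, with no hypothesis, comparison or sample size, and serious events are protected. That makes this a should-fix.

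**What to change.** In SAP 11.1, define treatment emergence by event:

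1. An AE counts if its onset is on or after the first open-label dose and no later than 30 days after the last.
2. An AE also counts if it was ongoing at the first open-label dose and then increased in severity or became serious.
3. The severity benchmark uses only AEs of that term ongoing at the first open-label dose.
4. A resolved earlier AE does not suppress a recurrence.
5. Add a rule for missing or partial AE stop dates. SAP 16.7 imputes AE start dates only, and the stop-date rules in SAP 16.8.2 are for medications. One option is to treat an earlier AE as ongoing only when its stop date is missing or not before the first open-label dose, and to say how a partial date is handled.

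Make the edit together with the reference-date correction in the same sentence, and record it in SAP 17.0 as a change from Protocol 9.7.6.1.

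The cost is SAP wording and a small amount of programming, with no added visits or assessments. The completeness of stop dates for AEs carried over from the lead-in studies cannot be verified from these documents and should be checked first. Reported TEAE percentages will be slightly higher.
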